4.4.1 Primary Endpoint

4.4.1.1 Primary Endpoint Definition

The primary analysis will be based on safety population.

The primary analysis will be based on the number of subjects with potential sensitization reactions considered photo-initiated (i.e. potential photo-sensitization reactions).

Potential photo-sensitization reactions are defined as a positive reactions meeting both of the following requirements:

- sensitization reported as “yes” at final visit of challenge phase (sensitization box ticked “yes” on eCRF)
- the maximum score of the UV-exposed site (across all visits) during the challenge phase > maximum score of the non-UV exposed site (across all visits) during the challenge phase

The number and percentage of subjects with potential sensitization considered photo- initiated reactions will be presented by product group in [Table 14.2.2.1](#). No formal statistical inference will be performed.

All potential sensitization reactions considered photo-initiated will be listed ([Listing 16.2.6.3](#)) for the safety population.

A frequency table will be presented for potential sensitization reactions (Sensitization (Yes), non-sensitization (No) and Unable to determine) regardless of photo initiation status by product group in [Table 14.2.1.1](#).

4.4.1.2 Statistical Hypothesis, Model, and Method of Analysis

No formal statistical inference is planned for primary endpoint.

4.4.1.3 Supportive Analyses

N/A

4.4.2 Secondary Efficacy Variables

Secondary endpoint variables are defined in [Section 4.5](#).

4.4.3 Handling of Missing Values/Censoring/Discontinuations

Missing data will not be replaced or imputed. Dropouts will be included in analyses up to the point of discontinuation.

4.5 Analysis of Secondary Endpoints

The secondary analysis will be based on safety population. The secondary endpoints will be derived based on the ICDRG scores and the investigator assessment of potential sensitization as described in [Section 4.4](#).

4.5.1 Secondary Endpoint

Evaluation of the cutaneous photo-irritation potential:

- Potential photo-irritation reactions (photo-initiated reactions that are not considered a potential sensitization reaction) are defined as positive reactions meeting both of the following requirements: sensitization reported as “No” or “Unable to determine” or missing at final visit of challenge phase (sensitization box ticked “No” or “Unable to determine” or missing on eCRF)
- the maximum score of the UV-exposed site (across all visits) during the induction and challenge phase > maximum score of the non-UV exposed site (across all visits) during the induction and challenge phase

The number and percentage of subjects with photo-initiated reaction that is not considered a potential sensitization reaction will be presented by product group in [Table 14.2.2.1](#). No formal statistical inference will be performed.

All photo-initiated reactions that are not considered as potential sensitization reactions, will be Listed ([Listing 16.2.6.4](#)) for the safety population.

Evaluation of the cutaneous sensitization potential:

Potential sensitization reactions not considered photo-initiated are defined as positive reactions meeting both of the following requirements:

- sensitization is equal to “Yes” at final visit of challenge phase (sensitization box ticked “Yes” on eCRF)
- the maximum score of the UV-exposed site (across all visits) during the challenge phase \leq maximum score of the non-UV-exposed site (across all visits) during the challenge phase

The number and percentage of subjects with potential sensitization not considered photo-initiated will be presented by product group in [Table 14.2.2.1](#) using the maximum score. No formal statistical inference will be performed.

All potential sensitization reactions that are not considered photo-initiated will be listed ([Listing 16.2.6.5](#)) for the safety population.

Evaluation of the cutaneous irritation potential

Positive reactions not considered potential sensitization and not considered as photo-initiated are defined as positive reactions meeting both of the following requirements:

- sensitization reported as to “No” or “Unable to determine” or missing at final visit of challenge phase (sensitization box ticked “No” or “Unable to determine” or missing on eCRF)
- the maximum score of the UV-exposed site (across all visits) during the induction and challenge phase \leq maximum score of the non-UV exposed site (across all visits) during the induction and challenge phase

The number and percentage of subjects with positive reactions not considered potential sensitization and not considered as photo-initiated will be presented by product group in [Table 14.2.2.1](#) using the maximum score. No formal statistical inference will be performed.

All positive reactions not considered potential sensitization and not considered as photo-initiated, will be listed ([Listing 16.2.6.6](#)) for the safety population.

A listing will be presented for all the ICDRG grades in [Listing 16.2.6.1](#) and all positive reactions will be listed in [Listing 16.2.6.2](#).

Narrative descriptions of all positive reactions (scores of + or greater), in the challenge phase, will be provided in [Listing 16.2.6.7](#) for the safety population.

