The acute aspects of photo-irritant reactions may begin within a few minutes to hours after irradiation and tend to resolve within a few days to weeks. Whereas the acute aspects of photo-irritant reactions typically present soon after irradiation, photo- sensitisation reactions seldom occur after the first exposure to the photo-allergen. Since photo-sensitisation is an immunological process in nature, multiple exposures to the photo-activated allergen and a latent period of several days to weeks are typically required before the immune system is ready to respond. Once a subject has been sensitised, subsequent exposures to the photo-allergen and light will elicit cutaneous responses quite rapidly within 24-72 hours ([Beani 2017](#)).

A subject may experience positive reactions in any of the following patterns:

1. At ONLY the UV-exposed site,
2. At ONLY the Non-UV-exposed site,
3. At BOTH the UV-exposed and non-UV-exposed sites.

The location of positive reactions will be determined after unblinding to determine whether a reaction is potentially photo-initiated:

- Positive reactions which occur at ONLY the UV-exposed site will be considered photo-initiated.
- Positive reactions which occur at ONLY the non-UV-exposed site will not be considered photo-initiated.
- Positive reactions which occur at BOTH the UV-exposed and non-UV-exposed sites will be considered photo-initiated if the maximum score at the UV-exposed site is more severe than the maximum score at the non-UV-exposed site. If the maximum score at the UV-exposed site is equal to or lower than the non-UV-exposed site, then it will not be considered photo-initiated.

The inclusion of evaluations at 24, 48 and 72-hours for duplicate sites treated with study products, with or without UVR, in a cumulative application via an induction phase, latent rest phase, and challenge phase, permits simultaneous evaluation of the potential for contact irritation, photo-irritation, contact sensitisation and photo-sensitisation.

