### 8.4.1 Induction Phase Randomisation

Each subject will be assigned and identified by a unique Screening Subject Number sequentially as they sign their informed consent. Any reference made to an individual subject within the study must be done using their unique Screening Subject Number. This will remain the same for each subject throughout the study duration.

All subjects who meet the criteria for entry into the study will be centrally randomised using Interactive Response Technology (IRT). Before the study is initiated, training, login information and directions for the IRT will be provided to the study site. Study products will be dispensed according to the instruction received through the IRT system at the appropriate study visits.

Two semi-occlusive patches with 6 cells applied on the subject dorsum. Four cells (A, B, C and D) of the patch will be used in this study (3 cells for each of the test products and 1 cell for the reference product (saline solution). The two cells E and F will always remain empty. See also [5.4 Randomisation Criteria](#) and [6.1.2 Preparation and Dispensing](#).

At Visit 4, a randomisation number will be assigned electronically in ascending numerical order to each subject who is determined to be fully eligible. This randomisation number will include

the sites of applications on the patch of each treatment. The sites of application will be the same for the two patches (UV-irradiated, non-UV-irradiated).

The randomisation schedule for the induction phase will follow a 4x4 Latin Square (Williams) design. An example of a randomisation schedule for the induction phase is shown below:

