### 8.10.1 Challenge Phase Randomisation

At visit 19, another randomisation number will be assigned to each subject that completed the induction phase using the IRT system. This randomisation number will be different from the one previously assigned at Visit 4 and will include the sites of applications of each treatment for the challenge phase. The test sites of study products application will be previously untreated (naive) skin sites in the back, between shoulder blade and waistline for the duplicate UV-irradiated and non-UV-irradiated patch systems.

Randomisation schedule for the challenge phase will follow a 4x4 Latin Square (Williams) design. An example of the randomisation schedule is shown below:

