**Table 8-2 Application site sequences- challenge phase**

Randomisation Number	Patch cell	Challenge phase (same sequence to be used for the UV-irradiated, non-UV-irradiated patches)			
		Cell A	Cell B	Cell C	Cell D
PPD		Test Product 2	Test Product 3	Test Product 1	Reference product
PPD		Reference product	Test Product 1	Test Product 3	Test Product 2
PPD		Test Product 3	Reference product	Test Product 2	Test Product 1
PPD		Test Product 1	Test Product 2	Reference product	Test Product 3

Please refer to section [8.4 \(Induction Phase Day 1 Visit 4 Monday\)](#) for assessments on this day.

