#### *Evaluation of the cutaneous photo-irritation potential*

The classification of a positive reaction as a photo-initiated reaction will use the same criteria described in the primary endpoint.

The number and percentage of subjects with any photo-initiated reaction that is not considered a potential sensitisation reaction, versus those without a reaction will be presented by treatment group. No formal statistical inference will be performed.

All photo-initiated reactions that are not considered as potential sensitisation reactions, will be listed.

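### SAP 4.5.1 pools induction and challenge maxima, so a subject with a photo-initiated reaction in one phase and a non-photo reaction in the other counts in only one irritation row

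*SAP*

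**What the plan says.** SAP 4.5.1 places a subject without a 'Yes' for sensitisation in the photo-irritation row if "the maximum score of the UV-exposed site (across all visits) during the induction and challenge phase" exceeds the "maximum score of the non-UV exposed site (across all visits) during the induction and challenge phase". The irritation row uses the same two maxima with the opposite condition (UV less than or equal to non-UV). SAP 4.4 confirms that the maximum runs over all available visits in whichever phase or phases the endpoint names, and that the subject is the unit classified.

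The primary endpoint uses a different window. SAP 4.4.1.1 requires "the maximum score of the UV-exposed site (across all visits) during the challenge phase > maximum score of the non-UV exposed site", both in challenge only, and the sensitisation row in SAP 4.5.1 does the same.

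Protocol 12.2.7 says of photo-irritation: "The classification of a positive reaction as a photo-initiated reaction will use the same criteria described in the primary endpoint". It counts subjects with any such reaction that is not potential sensitisation. The underlying rule in Protocol 4.2 and 12.2.6 begins: "Positive reactions which occur at ONLY the UV-exposed site will be considered photo-initiated". A reaction at both sites is photo-initiated only if the UV maximum is the more severe. The protocol names no phase for that comparison.

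On the design, Protocol 8.4.1 puts each product in the same cells of the two induction patches, and Table 8-2 does so for challenge ("same sequence to be used for the UV-irradiated, non-UV-irradiated patches"). Challenge is on previously untreated skin under a new randomisation; Protocol 8.10.1 says "This randomisation number will be different from the one previously assigned at Visit 4". Protocol section 1 and SAP section 1 both place the evaluation of photo-irritation primarily in induction.

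**The concern.** The non-UV site is the control for the UV site carrying the same product in the same phase. Pooling breaks that pairing: an induction UV score can be set against a non-UV score from a different area of skin weeks later. Because the two row conditions are exact complements on one pair of numbers, no subject can appear in both rows for a product, even with a genuine reaction of each type.

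This matters most for photo-irritation, where ties go to the non-photo row. A UV-only reaction in induction, the phase meant to be most informative, can vanish from the row that summarises it. It would also be missing from Listing 16.2.6.4, which covers the same category. In a safety study, a rule that can only lower these counts deserves attention.

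The same label also carries two windows. The photo-initiated status of one challenge reaction can depend on how the dermatologist answers the separate question about sensitisation.

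**Working it through.** **Inputs.** Five ordered scores (SAP 4.4): '-' < '+?' < '+' < '++' < '+++', with '+' or higher positive. Sensitisation answer not 'Yes'. At least 40 randomised and at least 25 evaluable completers (SAP 1.4). The plan gives no figure for this point, so there is none to reproduce.

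**1. Worked examples (one subject, one product).**

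| Induction UV / non-UV | Challenge UV / non-UV | By phase | Pooled maxima | SAP row |
|---|---|---|---|---|
| '+' / '-' | '+' / '+' | photo, then non-photo | '+' vs '+' | irritation only |
| '++' / '-' | '+' / '+' | photo, then non-photo | '++' vs '+' | photo-irritation only |
| '-' / '+' | '+' / '-' | non-photo, then photo | '+' vs '+' | irritation only |

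In the third case the challenge reaction is photo-initiated if answered 'Yes' (challenge window), but not if answered 'No' (pooled window).

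**2. All patterns.** Each phase has 5 × 5 = 25 combinations of UV and non-UV maxima.

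- Photo-initiated (UV at least '+', UV > non-UV): 2 + 3 + 4 = 9.
- Non-photo (non-UV at least '+', UV ≤ non-UV): 3 + 4 + 5 = 12.
- No positive: 4.

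Over two phases there are 25² = 625 patterns.

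- Photo-initiated in either phase: 625 − 16² = 369.
- Non-photo in either phase: 625 − 13² = 456.
- One of each: 2 × 9 × 12 = 216.

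Under pooling, a maximum at level k (0 to 4) arises in 2k + 1 ways from two scores.

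- Pooled photo-initiated: 5 × 4 + 7 × 9 + 9 × 16 = 227. Lost: 369 − 227 = 142.
- Pooled non-photo: 5 × 9 + 7 × 16 + 9 × 25 = 382. Lost: 456 − 382 = 74.
- Check: 142 + 74 = 216.

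No pattern is falsely added to a row. If the pooled UV maximum is positive and exceeds the pooled non-UV maximum, the phase that supplied it is itself photo-initiated; the non-photo row follows in the same way.

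**3. Milder scores only.**

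| Highest score | Patterns | Photo-initiated lost | Non-photo lost |
|---|---|---|---|
| '+' | 81 | 12 of 32 | 0 of 45 |
| '++' | 256 | 52 of 135 | 18 of 175 |
| '+++' | 625 | 142 of 369 | 74 of 456 |

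Comparing the challenge-only window with the pooled one for a challenge reaction, the label changes in 71 of 225 photo-initiated patterns and 37 of 300 non-photo patterns.

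**4. Expected subjects lost from photo-irritation.** Let a be the proportion with a photo-initiated reaction in a phase, and r the proportion of those in whom a non-UV score in the other phase reaches the pooled UV maximum. Both are assumptions. Expected loss = 2 × n × a × r.

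- n = 25, a = r = 2%: 0.02.
- a = r = 5%: 0.125 (n = 25) or 0.2 (n = 40).
- n = 40, a = r = 10%: 0.8.

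One subject moves a row by 1/40 = 2.5 or 1/25 = 4 percentage points.

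**5. Chance flags under per-phase derivation.** Assume no UV effect and independent '+' scores with probability p per site and phase. Per phase: 1 − (1 − p(1 − p))². Pooled: q(1 − q), with q = 1 − (1 − p)².

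| p | Per phase | Pooled | Extra subjects of 40 |
|---|---|---|---|
| 2% | 3.9% | 3.8% | 0.03 |
| 5% | 9.3% | 8.8% | 0.19 |
| 10% | 17.2% | 15.4% | 0.72 |

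The irritation count does not change in this calculation.

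**The case against.** The window is pre-specified and visible. Protocol 12.2 leaves analysis detail to the SAP, SAP 4.4 explains the maximum, and SAP 4.5.1 names the phases. Protocol 4.2 introduces its reaction patterns at subject level, so the first example could be read as a both-sites tie; Protocol 12.2.7 also presents the irritation row by maximum score. A difference in window has a reason, since sensitisation is judged only from challenge while irritation can arise in either phase. Some offsetting remains within induction too, across six applications, and matching there is imperfect because a strong reaction moves the next patch. The assumed rates have no source.

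Much of this stands. Because the protocol names no phase, pooling adds a specification and does not contradict the SAP's statement that nothing changed. Irritation also needs a wider window than sensitisation. But using both phases does not require merging them before the comparison, and the protocol's count of subjects with any photo-initiated reaction favours the per-phase reading. Offsetting within a phase follows the protocol's maximum rule and at least compares the two patch series of that phase; pooling across phases does not.

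The numerical caveats also stand. The patterns are unweighted and assume all four maxima are available. The expected loss stays below one only within the chosen range: n = 40, a = 10% and r = 30% gives 2 × 40 × 0.10 × 0.30 = 2.4.

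**Conclusion.** The concern holds and is minor. Followed exactly, SAP 4.5.1 drops genuine reactions from one irritation row whenever the other phase offsets them. With complete data it can lower each of the two counts but never raise them, for test products and saline alike. When no score exceeds '+', every loss is from photo-irritation.

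The practical size is probably well below one subject per product, because the documents expect the vast majority of responses to be negative; this rests on the assumed 2–10% rates. Each affected subject still appears in one irritation row, and Listings 16.2.6.1 and 16.2.6.2 allow a per-phase count to be rebuilt. There is no formal inference, and the primary endpoint and success criterion are untouched. The point does not concern subjects answered 'Yes', who are in neither irritation row.

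**What to change.** In SAP 4.5.1, compare the UV and non-UV maxima within each phase, separately for each product. Count a subject in a row if either phase qualifies, and state that a subject may appear in both rows. Show induction and challenge separately in Table 14.2.2.1, unless the display list in Attachment 1 (not visible in the text reviewed) already does so, and apply the same definitions to Listings 16.2.6.4 and 16.2.6.6. Taking the maximum across visits within a phase should stay, as should the challenge-only window for the primary and sensitisation rows.

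The cost is a change of wording, minor programming, and rows that overlap and so no longer sum. Chance photo-irritation flags rise by about 0.1, 0.5 or 1.8 percentage points at '+' rates of 2%, 5% or 10%, equally for saline, so the comparison with the reference remains fair.

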4.5.2 Pharmacokinetic (Secondary)

N/A.

4.6 Analysis of Safety

All safety data will be reported for the Safety Population as per actual product received. The safety profile of the study products will be assessed with respect to AEs.

4.6.1 Adverse Events and Serious Adverse Events

All AEs will be reviewed by the Clinical Research Scientist or Designee prior to database lock and will be coded to a system organ class (SOC) and preferred term (PT) using the Medical Dictionary for Regulatory Activities (MedDRA).

AEs will be classified as skin and non-skin on the AE page of eCRF.

Treatment emergent adverse events (TEAEs) are defined as new AEs that occur on or after the start date of study product (if this date is missing a suitable alternative will be used e.g., date of randomization in induction phase). Adverse events with an onset date/time prior to the first product application will be considered as non-treatment emergent.

The following summary tables and listings will be presented by product group and overall.

- Table of treatment emergent AEs by system organ class (SOC) and Preferred Term (PT) ([Table 14.3.1.1](#)). Summary of the number and percentage of subjects with at least one AE, total number of AEs, number and percentage of AEs within each SOC and PT will be displayed.
- Table of treatment-related treatment emergent AEs by SOC and PT ([Table 14.3.1.3](#))
- Table of treatment emergent AEs by Skin/Non-Skin and PT ([Table 14.3.1.2](#))
- Table of treatment-related treatment emergent AEs by Skin/Non-Skin and PT ([Table 14.3.1.4](#))
- Table of treatment emergent serious adverse events (SAEs) by SOC and PT ([Table 14.3.1.5](#)) [only produced if there are more than 5 SAEs].
- Table of treatment emergent AEs by SOC, PT, and severity ([Table 14.3.1.6](#))
- Table of treatment-related treatment emergent AEs by SOC, PT, and severity ([Table 14.3.1.7](#))
- Listing of all AEs ([Listing 16.2.7.1](#) for all randomized subjects; [Listing 16.2.7.2](#) for non-randomized subjects)
- Listing of deaths ([Listing 14.3.2.1](#))
- Listing of non-fatal SAEs ([Listing 14.3.2.2](#))
- Listing of treatment-emergent AEs leading to study or drug withdrawal ([Listing 14.3.2.3](#))
- Listing of treatment-emergent AEs by Skin/Non-Skin ([Listing 14.3.2.4](#))

In the event that there is nothing to report, a null table or listing will be produced.

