### **12.2.8 Safety Analysis(es)**

Safety analyses will be performed using the safety population according to the treatment that the subject received. Adverse events (AEs) will be coded using the Medical Dictionary for Regulatory Activities (MedDRA).

AEs will be regarded as treatment emergent if they occur on or after the first treatment application.

Treatment Emergent Adverse Events (by System Organ Class/Preferred Term), Treatment Emergent Adverse Events (skin site related/non-skin site related), treatment-related AEs (skin site related/non-skin site related) will be summarised overall and by treatment group.

Deaths, Non-fatal Serious Adverse Events, Treatment Emergent Adverse Events leading to study or drug discontinuation will be listed.

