1.2 Study Objectives

The study objectives are as follows:

Objectives	Endpoints
Primary Objective	Primary Endpoint
To evaluate the cutaneous photo-Sensitization potential of three cosmetic facial skincare products compared to saline solution.	Proportion of subjects with a potential sensitization reaction which is considered photo-initiated.
Secondary Objectives	Secondary Endpoints
To evaluate the cutaneous photo-irritation potential of three cosmetic facial skincare products compared to saline solution.	Proportion of subjects with a photo-initiated reaction score of '+' or greater which not considered a potential sensitization reaction.
To evaluate the cutaneous sensitization potential of three cosmetic facial skincare products compared to saline solution.	Proportion of subjects with a potential sensitization reaction which is not considered photo-initiated.
To evaluate the cutaneous irritation potential of three cosmetic facial skincare products compared to saline solution.	Proportion of subjects with a non-photo-initiated reaction score of '+' or greater which is not considered a potential sensitization reaction.
Safety	
To evaluate the general safety of three cosmetic facial skincare products	Frequency and severity of Adverse Events

Success criteria:

A test product will be considered to have low photo-sensitization potential if the proportion of subjects with a potential photo-sensitization reaction are comparable for the test product and saline.

The hypothesis is that the study products will have low photo-sensitization potential. Therefore, it is expected that the vast majority of responses will be negative. No formal statistical comparison between product groups shall be made.

Developmental cosmetic moisturizers (a serum, lotion and cream)

212378

Statistical Reporting and Analysis plan Amendment 1, Text Final v1.0, 03 Sep 2019

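### SAP 4.6.1 puts AEs, not subjects, in the SOC and PT rows of Table 14.3.1.1 with no denominator, and gives no counting unit for the other six AE tables

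*SAP*

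**What the plan says.** The safety endpoint in SAP 1.2 and protocol Table 3-1 is "Frequency and severity of Adverse Events"; neither place says whether frequency means events or people.

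SAP 4.6.1 introduces the AE displays with "The following summary tables and listings will be presented by product group and overall". It describes the content of only one of them, Table 14.3.1.1. That description starts with subjects, "Summary of the number and percentage of subjects with at least one AE", and then changes unit for the body of the table: "total number of AEs, number and percentage of AEs within each SOC and PT will be displayed". No base is given for the second percentage.

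The other six AE tables, 14.3.1.2 to 14.3.1.7, have a title and nothing on the counting unit; 14.3.1.3, for example, is "Table of treatment-related treatment emergent AEs by SOC and PT". Protocol 12.2.8 does not settle it either. It says only that such events, including "treatment-related AEs (skin site related/non-skin site related) will be summarised overall and by treatment group".

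The reaction endpoints are handled differently. SAP 4.4.1.1 names the unit: "The number and percentage of subjects with potential sensitization considered photo- initiated reactions will be presented by product group". SAP 4.1.1 likewise gives denominators for the disposition percentages.

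**The concern.** A safety table by SOC and PT is normally read as the proportion of people who had each kind of event. A number and percentage of AEs does not answer that question. If the base is all AEs, the figure is a share of reports: it moves with the number of unrelated events, and it counts a recurrent event as often as it recurs. If the base is the number of subjects, the figure looks like an incidence but is not one.

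In a sample planned at no fewer than 40 randomised subjects, one person with several records of the same term could put that term at the top of the table. What is at stake is how the general safety summary reads. The photo-sensitisation conclusion does not depend on it.

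**Working it through.** The plan has no AE figure to reproduce: it gives no AE rate, and SAP 1.4 says no power calculation was made. The check therefore takes the stated unit and works out what it does.

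**Inputs from the documents**
- SOC and PT rows of Table 14.3.1.1: number and percentage of AEs, base not stated (SAP 4.6.1).
- Any-AE line of the same table: subjects (SAP 4.6.1).
- Subjects: at least 40 randomised, at least 25 evaluable completers (SAP 1.4).

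**Assumed inputs (illustration only)**
- Term A: one subject with k episodes.
- Term B: m subjects with one episode each.
- No other AEs, so total AEs = k + m.

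**Formulas**
- Share of AEs: A = k/(k + m), B = m/(k + m).
- Events over subjects: A = k/N, B = m/N.
- Subject incidence: A = 1/N, B = m/N.

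On either event-based percentage, A ranks above B exactly when k > m, because both terms share a denominator. On subject incidence, B ranks above A whenever m is at least 2. The order therefore reverses when k > m and m is at least 2.

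**Results, N = 40**

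| k | m | Share of AEs, A v B | Events/N, A v B | Subjects, A v B | Order reversed? |
|---|---|---|---|---|---|
| 6 | 4 | 6/10 = 60% v 4/10 = 40% | 6/40 = 15% v 4/40 = 10% | 1/40 = 2.5% v 4/40 = 10% | yes |
| 4 | 3 | 4/7 = 57.1% v 3/7 = 42.9% | 10% v 7.5% | 2.5% v 7.5% | yes |
| 3 | 2 | 3/5 = 60% v 2/5 = 40% | 7.5% v 5% | 2.5% v 5% | yes |
| 3 | 3 | 50% v 50% | 7.5% v 7.5% | 2.5% v 7.5% | tie on events |
| 2 | 3 | 40% v 60% | 5% v 7.5% | 2.5% v 7.5% | no |

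The result does not depend on N. At N = 25, k = 4 and m = 3 give 57.1% v 42.9% of AEs and 16% v 12% on events over N, but 4% v 12% of subjects.

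The second base can also mislead without any ranking. Four episodes in one subject of 40 would print as 4/40 = 10%, where the incidence is 1/40 = 2.5%.

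**Does another section supply the missing statistic?** SAP 1.2, SAP 4.6, protocol Table 3-1 and protocol 12.2.8 were read for a subject count by term, a rule of one count per term, or a highest-severity rule. None contains one.

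**The case against.** Several stronger readings are tempting, and the documents do not support them.

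- **That none of the safety tables gives subject incidence by event type.** The quoted sentence belongs to Table 14.3.1.1 alone. For the other six the unit is unstated, which does not show that events will be counted. Attachment 1 is named, but its content was not available, so the layouts may settle the matter.
- **That the severity tables, 14.3.1.6 and 14.3.1.7, would count each mild and severe record of one subject separately.** This too would be an inference from silence.
- **That 60% v 40% is what the plan prescribes.** No denominator is given, so those figures hold only if the base is total AEs.
- **That repeated records are likely.** AEs are asked about at every visit, but the protocol has the diagnosis recorded where known (10.4) and events followed to resolution or stabilisation (10.6). Patch-area reactions that the ICDRG scale fully describes are kept out of AE recording (8.5.2, 9.2.1, 10.1). Repeats are possible; no rate is given. Without repeats, event and subject counts within a term agree.

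The SAP sentence is also loosely punctuated. A less natural reading lets the SOC and PT qualifier govern the whole list, including the subject count, so this may be unclear drafting and not a decision to leave subject counts out. Even so, the denominator, the once-per-term rule and the highest-severity rule would still be missing, and the same edit would be needed.

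The case for limited impact stands. The endpoint wording does not exclude event counts. The success criterion rests on potential photo-sensitisation reactions, which are counted by subject. SAP 4.6.1 also provides "Listing of all AEs", from which incidence by term could be worked out by hand at this sample size.

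**Conclusion.** The point holds for Table 14.3.1.1. Its SOC and PT rows are specified as events with an undefined percentage, and nothing in the available text adds subject incidence by term. For Tables 14.3.1.2 to 14.3.1.7 the supportable statement is narrower: the counting unit is not given.

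The ranking consequence is exact arithmetic once one subject's episodes outnumber the subjects who had the other term, and it applies to either candidate base. The size of any distortion rests on assumed AE counts and cannot be predicted from the documents.

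The importance is low. No formal inference is planned, the any-AE line already counts subjects, and no data are lost. It remains worth correcting because a better statistic is available from data already being collected.

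**What to change.** Replace the description under Table 14.3.1.1 in SAP 4.6.1 with a rule that covers Tables 14.3.1.1 to 14.3.1.7, along these lines:

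- Each SOC and PT row shows the number and percentage of Safety-population subjects with at least one event, and the number of events.
- A subject is counted once per SOC and once per PT, within each product column and overall. The denominator is the number of Safety-population subjects in that column.
- In Tables 14.3.1.6 and 14.3.1.7 a subject is counted at the highest severity reported for that SOC or PT.
- In Tables 14.3.1.2 and 14.3.1.4 the same counting applies within the skin and non-skin categories.

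Check the layouts in Attachment 1 against this rule and align them where they differ.

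The cost is a few lines of SAP text and any matching change to the table layouts. Event counts stay in the tables, no new data are needed, and no other analysis is affected.
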